5.5. Treatment Randomization, Instructions, Adherence Strategies. Following baseline, participants will be randomized to one of three 16-wk treatments: (1) **Exercise Alone** (n=30) (**5.5.1**); (2) **Weight Loss Alone** (n=30) (**5.5.2**); or (3) **Exercise + Weight Loss** (n=30) (**5.5.3**). Randomization will be stratified by age (< vs. ≥ 40), sex, and severity of screening AHI (10-25 or > 25) in blocks of 6, using a computer-generated list.

The duration of the intervention was chosen so that there would be sufficient time to detect chronic adaptations to the interventions without placing undue burden on the participants. Sixteen weeks is sufficient time to detect chronic exercise benefits¹⁴ and to achieve the targeted weight loss using the moderately challenging proposed procedures. Following randomization, treatment expectancy for changes in OSA severity, sleep quality, daytime sleepiness, mood, and health will be assessed via 5-point Likert scales.

Lifestyle Activity and Eating. Because lifestyle changes could mask the effects of the experimental exercise and weight loss, participants will be asked to maintain their normal activity and eating habits, except as prescribed for the study. In our previous trial, such requests were followed, as evidenced by the lack of weight loss¹⁹ and the proposed monitoring methods.

To monitor changes in unsupervised physical activity, participants will wear a waist accelerometer from baseline through the post-intervention assessment (except during experimental exercise). This device has been validated against energy expenditure estimated with oxygen consumption and doubly labeled water. It records daily steps and time spent in light, moderate, and vigorous activity. Data will be analyzed in 2-wk bins.

Food intake will be assessed with the Automated Self-Administered 24-hr diet recall (ASA24) (<http://riskfactor.cancer.gov/tools/instruments/asa24/>), to be completed twice during baseline and during Weeks 8 and 16 of treatment. The recall is among the highest quality with the least bias and subject burden.

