1. 5-Day home sleep (actigraphy/diary) 2.1-Night PSG-Apnea, HRV 3. Weight/DEXA 4.Blood pressure 5. Insulin, glucose, hemoglobin A1c, lipids 6. Inflammation 7. ASA24-Diet Recall 8. FOSQ, PSQI, snoring	Wks 4, 8, 12, 16: FOSQ, PSQI, snoring End of Wk 8: ASA24 Wks 5, 10: Physical: blood pressure, insulin, glucose, and hemoglobin a1c	1. 5-Day home sleep (actigraphy/diary) 2.1-Night PSG-Apnea, HRV 3. Weight/DEXA 4.Blood pressure 5. Insulin, glucose, hemoglobin A1c, lipids 6. Inflammation 7. ASA24 8. FOSQ, PSQI, snoring
Waist Actigraphic Assessment of Activity		
Key. PSG-Polysomnography, DEXA-Body Composition, FOSQ-Functional Outcomes of Sleepiness; PSQI-Pittsburgh Sleep Quality Inventory, ASA24-Dietary Recall		

5.6.1. Sleep and OSA Assessment. Both at baseline and following completion of the 16-week intervention, sleep will be assessed objectively for 5 days/nights in the home and for 1 night in the sleep laboratory.

Home Recording. Participants will be asked to maintain their sleep habits. Sleep will be assessed with wrist actigraphs, which are used to estimate sleep/wakefulness based upon validated algorithms associating wrist movement with PSG. Actigraphy probably provides the best measure of daytime napping, an indication of sleepiness. Measures will include sleep onset latency, wakefulness after sleep onset, time in bed (TIB), total sleep time (TST), sleep efficiency (SE), and daytime napping. Sleep apnea will be assessed with the ARES on the last night of assessment at the end of the intervention and then compared with screening and follow-up.

Actigraphic data will be supplemented with a daily sleep diary, which will assess subjective perceptions of sleep onset latency, wake time after sleep onset, time in bed, total sleep time, insomnia, and sleep quality.

Self-reported sleep measures are also deemed important indications of treatment effects. Actigraphic and sleep diary data will be averaged over the 5 days of assessment by an investigator blinded to treatment. Subjective sleep will also be assessed with the Pittsburgh Sleep Quality Inventory,¹¹⁹ as described in **5.6.3**.

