Snoring Symptoms Inventory. In our previous study, anecdotal reports indicated that exercise substantially reduced snoring, which could have significant health implications even in the absence of improvement in OSA. This 25-item scale has been sensitive to uvulopalatoplasty. Also, bed partners or housemates of participants will be asked to assess snoring changes (from 1=much better to 5=much worse).

5.6.4. Physical Examinations during the Intervention. At Weeks 5 and 10 of the intervention, participants’ health will be monitored by a brief physical examination, including blood pressure and fasting assessment of glucose, insulin, and hemoglobin a1c. Physician judgment of significant health deterioration or significant impairments in these variables at these time points will result in exclusion from the study.

5.7. Follow-Up Assessments. Three months after completion of the intervention, participants will undergo another night of home OSA assessment with the ARES. Participants will also return to the laboratory to assess body weight and and completes several questionnaires, including the **PSQI, FOSQ, Snoring Symptoms Inventory, physical activity recall, involvement in PAP and other treatments, and 24-hr dietary recall.**

5.8. Compensation. Participants will receive \$400 after the post-study measures. Pro-rated pay for drop-outs will be \$40 for screening; \$20 per week of the study; and \$20 for follow-up. The Exercise Alone and Weight Loss Alone groups will have the opportunity to receive the other intervention free of charge following the study.

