5.10. Statistical Analysis. We will first examine univariate and bivariate statistics to determine the distributional characteristics of study variables and to identify potentially relevant background covariates and confounders. For the **Primary Hypothesis and Secondary Hypotheses 1 and 3**, we will use an analysis of covariance (ANCOVA) approach to examine treatment effects on post-intervention (i.e., immediate post-test for Primary Hypothesis and Secondary Hypothesis 3; 3-month follow-up for Secondary Hypothesis 1) outcome values (i.e., AHI scores for Primary Hypothesis and Secondary Hypothesis 1; comorbidity measures for Secondary Hypothesis 3), with treatment as the primary independent variable, and adjusting for baseline outcome value, intervention dose (percentage of sessions attended), baseline outcome value, age, sex,

duration of OSA diagnosis, plus any other relevant covariates. We will test for ordering of treatment means (not adjusted for covariates) via order-restricted tests within the R package flexisoreg. Next, we will test for overall differences among treatment groups on post-treatment AHI values with order-restricted comparisons (isotonic contrasts) of covariate-adjusted means to test for the predicted ordered patterning of the three treatment means. For **Secondary Hypothesis 2**, we will examine the effect of time point (pre- vs. post-treatment) on AHI scores at each treatment level (i.e., test “simple main effects” of time) in the context of a repeated measures ANCOVA. Analyses will be based on an intent-to-treat plan. For each hypothesis, overall alpha will be set at .05, with a Bonferroni correction applied when multiple non-independent tests are conducted. **Missing data** due to dropout or other causes will be addressed with analyses of multiply-imputed datasets generated with SAS PROC MI based on models drawing on all available participant data.

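### Section 5.6.4 excludes randomised participants from the study at Week 5 or 10 on health grounds; followed as written, their post-baseline AHI would be imputed although it could be measured

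*Combined protocol and SAP*

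**What the plan says.** Section 5.6.4 provides brief physical examinations at Weeks 5 and 10 covering blood pressure, glucose, insulin and hemoglobin A1c. It then says: "Physician judgment of significant health deterioration or significant impairments in these variables at these time points will result in exclusion from the study". No threshold for impairment is given.

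The AHI assessments are placed as follows.

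- Section 5.6.1, for the PSG that supplies the primary outcome: "Both at baseline and following completion of the 16-week intervention, sleep will be assessed objectively".
- Section 5.7, for Secondary Hypothesis 1: "Three months after completion of the intervention, participants will undergo another night of home OSA assessment with the ARES".

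Section 5.8 deals with people who leave early ("Pro-rated pay for drop-outs will be" followed by amounts for screening, for weeks in the study and for follow-up). It schedules no assessment for them.

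Section 5.10 states "Analyses will be based on an intent-to-treat plan". Missing data from dropout or other causes are to be handled with "multiply-imputed datasets generated with SAS PROC MI based on models drawing on all available participant data". The ANCOVA adjusts, among other things, for "intervention dose (percentage of sessions attended"). No sensitivity analysis for missing data is described.

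**The concern.** Stopping exercise or calorie restriction for safety does not in itself prevent a sleep recording. A rule that ends study participation, rather than the intervention, can therefore give up primary-outcome data that the trial could still collect.

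The loss would be linked to health and to a shortened intervention, so these participants may differ from completers in the outcome itself. The AHI comparison would then depend, for them, on how well earlier data predict AHI after stopping, and the trial could not check that. Post-baseline AHI not recorded at the time cannot be recovered later.

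The concern is specific to AHI. For blood pressure and hemoglobin A1c, the Week 5 and Week 10 values are themselves recorded and can inform the imputation.

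**Working it through.** **1. What is scheduled for someone excluded at Week 5 or 10.**

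| Assessment | Where | Timing | Scheduled for an excluded participant? |
|---|---|---|---|
| Home ARES, screening | 5.3.1.3 | before randomisation | already done |
| Laboratory PSG, baseline | 5.6.1 | before randomisation | already done |
| Laboratory PSG, post-treatment | 5.6.1 | after completing 16 weeks | no provision |
| Home ARES, end of intervention | 5.6.1 | end of intervention | no provision |
| Home ARES, follow-up | 5.7 | 3 months after completion | no provision |

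**2. What the imputation could use.** Screening and baseline AHI are available for everyone randomised. Interim data come from sections 5.5 to 5.6.4 and Table 2.

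- By Week 5: one questionnaire round, one examination and two complete 2-week accelerometer bins ("participants will wear a waist accelerometer from baseline through the post-intervention assessment"). There is also attendance, about 5 counselling reviews in the diet arms, and about 4 x 5 = 20 prescribed exercise sessions with heart-rate and workload data in the exercise arms.
- By Week 10: two questionnaire rounds, two examinations, the Week 8 diet recall, five bins, attendance, about 10 counselling reviews and about 4 x 10 = 40 prescribed sessions.

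None of the interim items is an AHI. The part of the 16 weeks left unobserved is 11/16 = 69% after a Week 5 exclusion and 6/16 = 38% after Week 10.

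**3. The plan's own power figure (5.9).** With a difference of 4, SD 5 and a two-sample t-test at one-sided 0.025, power is 86.1% at 30 per arm and 82.2% at 27. The plan states 86% and 82.2%, so both reproduce. If 1 or 2 further AHI values per arm were lost beyond the 10% allowance and contributed nothing, power would be 80.8% or 79.2%. The documents do not say whether health exclusions fall inside that allowance.

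**4. Illustration of bias in an unadjusted comparison.** Inputs from 5.9: planned AHI reductions of 14.9 (exercise + weight loss) and 10.9 (weight loss alone), a difference of 4, and 30 per arm. Assumptions, none of them in the documents: k participants are excluded; true benefit is proportional to weeks received; imputation removes a share R of the error that filling in the arm mean would make.

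Shift = k x planned reduction x (1 - weeks/16) x (1 - R) / 30

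- One Week 5 exclusion, exercise + weight loss only: 14.9 x 0.6875 / 30 = +0.34 at R = 0, +0.17 at R = 0.5, +0.07 at R = 0.8.
- Three such exclusions (10% of 30): +1.02, +0.51, +0.20.
- One Week 5 exclusion, weight loss alone only: -10.9 x 0.6875 / 30 = -0.25, -0.12, -0.05.
- Three at Week 5 in each arm: 3 x 4 x 0.6875 / 30 = +0.28 at R = 0, or 7% of 4.
- Week 10 instead of Week 5: multiply by 0.375/0.6875 = 0.55, so +0.19 for one in exercise + weight loss at R = 0.

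If all benefit were lost by Week 16, rather than kept in proportion, the first figure would be 14.9/30 = 0.50. For scale, the standard error of the contrast is 5 x sqrt(2/30) = 1.29.

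**5. The same scenario with attendance in the model.** The planned ANCOVA adjusts for attendance, which the arithmetic in step 4 omits. Two-arm simulations (30 per arm, SD 5, Week 5 exclusions in exercise + weight loss only, R = 0) compared measured with arm-mean-imputed AHI. The shift is 0.00 when everyone else attends fully. With variable attendance (for example an assumed SD of 10 percentage points), the shifts for one to three exclusions are about 0.12 to 0.25, or 3% to 6% of 4. These figures move with the attendance assumption and indicate an order of magnitude only.

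**The case against.** The strongest reply is that this matters little.

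- **Triggers should be rare.** Cardiovascular disease, diabetes and blood pressure above 159/99 are excluded at entry (Table 1 and 5.3.1.4). This stands.
- **The plan already keeps these people in the analysis.** A reader might infer that 5.6.4 contradicts intent-to-treat. It does not: 5.10 retains them by multiple imputation. The point is avoidable missing data.
- **Nothing says that measurement stops.** A reader might infer that AHI will certainly be missing. The documents support only a conditional statement. Section 5.8 pays early leavers for follow-up, so some contact is foreseen, and withdrawal terms may sit in consent pages that were not available. What remains is that no section schedules AHI for them.
- **The imputation has useful information.** It would be wrong to say that it rests on indirect data alone, since each participant has a screening and a baseline AHI and the exercise arms add session data. What is lacking is any AHI after baseline.
- **The arithmetic is not the planned analysis.** One, two or three Week 5 exclusions in exercise + weight loss give 0.34, 0.68 and 1.02 (9%, 17% and 26% of 4). A reader might take these as bias in the primary result. They apply to unadjusted arm means with no useful imputation. Whether adjusting for attendance is itself sound is a separate question.

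**Conclusion.** The point holds in conditional form. Section 5.6.4, read with 5.6.1 and 5.7, requires exclusion from the study and schedules no later AHI for those excluded. If it is followed as written, primary-outcome and 3-month AHI are lost for a health-related reason and replaced by imputation.

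The size is unknown and probably small. The documents give no exclusion rate, no trigger threshold and no correlation between interim data and AHI. The figure of up to 0.34 events/h per Week 5 exclusion in exercise + weight loss rests on proportional benefit, arm-mean imputation and no adjustment for attendance. Under the planned model the illustrated shifts are smaller. The direction depends on which arm loses people, and the documents do not settle that either.

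This is a cheap improvement to the protocol. It is not evidence that the primary analysis is invalid.

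**What to change.** - In 5.6.4, replace exclusion from the study with discontinuation of the study intervention. The physician's safety decision is unchanged.
- Subject to medical clearance and consent, invite these participants to the Week 16 PSG and laboratory visit and to the ARES 3 months later, both timed from randomisation. If the laboratory night is declined, offer the home ARES, which has a screening value for comparison.
- Analyse them in their randomised arm, and impute only where AHI is not obtained.
- Record by arm the reason and week of discontinuation and any start of positive airway pressure (PAP). Record AHI off PAP where clinically acceptable. Otherwise note its use, and run one sensitivity analysis that sets on-PAP values to missing.

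The cost is a change of wording, a few record items and a small number of extra assessments of non-completers, using visit types already in the schedule. Some will decline or will have started other treatment, so some imputation will remain.

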5.9. Sample Size and Power. The power calculations are based on our previous study and other published studies. We found an AHI reduction from 32.2 ± 5.6 SD to 24.6 ± 4.4 (7.6 or 24%) following a 12-week exercise protocol, and the attrition rate was 11%.¹⁹ The standard deviation of the change in AHI was large (13), perhaps because of the relatively short intervention duration and small sample size compared with what are proposed. In a recent meta analysis of the effect of dietary weight loss on AHI, we find an average reduction of AHI of 34% in studies involving weight loss of approximately 10% over intervention durations of 12-20 weeks.¹⁸ Based on this finding, we assume a reduction of total AHI from 32.2 ± 5.6 to 21.25 ± 5.2 following the Weight Loss Alone treatment (10.9 or ~34% reduction). A previous study indicated a 46% reduction in total AHI (from 21.7 ± 9.0 to 11.8 ± 6.8) following exercise and weight loss.²⁷ Based on these data, in calculating power, we assume decreases in AHI of increasing magnitude will be observed following exercise alone, weight loss alone, and exercise + weight loss. We assume a reduction of AHI from 32.2 ± 5.6 to 17.3 ± 5.2 (14.9 or 46% reduction) after exercise + weight loss, and we assume 10% attrition. In our power calculations, the overall significance level is set at $\alpha = 0.05$. To insure we will have sufficient testing power, order-restricted tests are not considered in power estimation, but this type of testing will be applied in our data analyses to test the hypothesized pattern.

To ensure power for the **Primary Hypothesis (Compared with exercise alone and weight loss alone, exercise+weight loss will elicit significantly greater improvements in AHI)** we consider weight loss alone vs. exercise+weight loss. We set the significance level at 0.025 to adjust for multiple testing. With $n=30$

per treatment, the power is 86% to detect an average difference of 4 (14.9 vs 10.9, or 46% vs 34%) in AHI reduction between the treatments assuming treatment standard deviations of 5. The power is 82.2% with a 10% attrition. We expect higher statistical power to compare exercise alone vs. exercise+weight loss.

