For **Secondary Hypothesis 1, Compared with exercise alone and weight loss alone, exercise + weight loss will elicit significantly greater improvements in OSA at 3-month follow-up**, we anticipate decreases in compliance, resulting in greater within-treatment variability and/or lower between-treatment differences, and less powerful between-treatment tests. As such, we consider 82% to be an upper bound power estimate of this hypothesis. If, for example, at follow-up, the magnitude of the effect of condition were only 80% of that anticipated at post-test, power to detect significant differences would be approximately 65%.

For **Secondary Hypothesis 2, Compared with baseline, each treatment will elicit significant improvements in AHI**, the power calculation is based on paired one-sided t-tests to test the reduction of AHI. Since there are 3 treatments, multiple-testing Bonferroni-adjusted significance level is set at $0.05/3=0.017$. For exercise alone, from our preliminary data, we set the mean±SD reduction in AHI (baseline minus post-treatment) at 7.6 ± 12.5 (24% reduction) for the power calculation. The standard deviation is smaller than in our preliminary study because of the longer duration and larger sample size. With $n=30$, tests should have power of 86.0% to detect such a post-exercise difference. With 10% attrition, our tests should have power of 82% to detect this change. Also, we propose a 16 wk treatment, which is a longer than in our previous study and may result in larger reduction with smaller variance. We expect that the AHI reduction will be at least as great as seen in our previous study. Because we expect that weight loss alone and exercise+weight loss will elicit larger effects than exercise alone, the power to detect changes in AHI will be greater for these other treatments.

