For **Secondary Hypothesis 3, Compared with exercise alone and weight loss alone, exercise + weight loss will elicit significantly greater improvements in measures of co-morbidity**, we use PSQI, systolic blood pressure, and hemoglobin a1c for power calculations. Power is estimated based on two-sample t-tests on the changes (post-treatment minus baseline) of each variable. Having repeated measures for some of these variables will further increase power. Similar treatment effects are assumed for weight loss alone and exercise alone. In this hypothesis, since the outcomes of interests were chosen based on previous studies instead of random selection, alpha for each test is set at 0.05. For Hypothesis 3, $n=30$ per treatment will result in power of ~80% on all the tests except for SBP with minimum detectable differences determined based on our preliminary data (**Table 3**). The power is close to 80% for PSQI and hemoglobin a1c, but 42-47% for systolic blood pressure, assuming 10% attrition. There is clearly sufficient power to detect baseline-to-post improvements for the co-morbidity variables following each individual treatment. Here we focus on effects of weight loss only and exercise only. At alpha of .05, for PSQI, the detectable average reduction is set at 1.5 with standard deviation of 1.8 (for both treatments). Estimated power is 99% with 30 subjects in each group and assuming 10% attrition. For SBP, power is 96% to detect a reduction of 6.7 with standard deviation of 10 with 30 subjects in the group and 10% attrition. Finally, for Ha1c, power is >.99 to detect an average reduction of 0.2% with standard deviation 0.1% assuming 10% attrition. In summary, with 30 subjects in each of the three treatment groups, we are confident that our tests will have power of 80% for most outcome variables.

Table 3. Statistical power under different reduction scenarios for Secondary Hypothesis 3.

PSQI *Reduction=1.5 SD _{diff} =1.8		SBP Reduction=6.7 SD _{diff} =10		Ha1c Reduction=0.2 (%) SD _{diff} =0.1 (%)	
#Diff	Power	Diff	Power	Diff (%)	Power
1.15	78.8%	3.8	42.5%	0.07	85.0%
1.26	85.0%	4.12	47.3%	0.077	90.4%

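### Fixed Bonferroni levels for the primary comparisons and Secondary Hypothesis 2 are valid but needlessly conservative; Holm's step-down keeps the same family-wise error and adds about 6 to 7 power points to the weaker primary comparison

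*Combined protocol and SAP*

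**What the plan says.** Section 5.9 opens its power calculations with an overall level: "In our power calculations, the overall significance level is set at" 0.05. For the Primary Hypothesis (the combined arm against each single treatment) it then says: "We set the significance level at 0.025 to adjust for multiple testing". The comparison it powers is weight loss alone versus the combined arm: "the power is 86% to detect an average difference of 4 (14.9 vs 10.9, or 46% vs 34%) in AHI reduction", "assuming treatment standard deviations of 5". It adds: "The power is 82.2% with a 10% attrition". Whether this test is one- or two-sided is not stated. No power figure is given for exercise alone versus the combined arm; the plan only expects it to be higher.

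For Secondary Hypothesis 2 (change from baseline within each arm), section 5.9 uses one-sided paired t-tests, and the "multiple-testing Bonferroni-adjusted significance level is set at" 0.05/3 = 0.017. Secondary Hypothesis 3 is treated differently: each test there is deliberately run at 0.05.

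Section 5.10 gives the general rule for each hypothesis: "overall alpha will be set at .05, with a Bonferroni correction applied when multiple non-independent tests are conducted". Neither section mentions a step-down procedure.

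**The concern.** Single-step Bonferroni holds every test in a family to the strictest level, even after other tests in that family have been rejected. Holm relaxes the level as rejections accumulate, with the same family-wise guarantee.

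The plan's own assumptions suit Holm well. It expects one large primary contrast (14.9 against 7.6) and one smaller one (14.9 against 10.9). If the large one is rejected at 0.025, Holm allows the smaller one to be tested at 0.05. The fixed rule keeps it at 0.025 and gains no additional error control from doing so. The same holds for exercise alone, the weakest of the three Secondary Hypothesis 2 tests. At stake is power on the comparison that drives the sample size.

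The wording also needs tidying. Section 5.10 corrects only non-independent tests, while the three within-arm tests of Secondary Hypothesis 2 use different participants. A literal reader could conclude that they go uncorrected, against section 5.9.

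**Working it through.** **Inputs (section 5.9).** Assumed AHI reductions: 7.6 (exercise alone), 10.9 (weight loss alone), 14.9 (combined). SD 5 per arm for the primary comparison; 7.6 with SD 12.5 for exercise alone in Secondary Hypothesis 2. The plan counts "with 30 subjects in each of the three treatment groups"; 10% attrition leaves 30 × 0.9 = 27.

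**Step 1: reproduce the primary power.** Two-sample t-test, noncentrality = 4 / (5 × √(2/n)), df = 2n − 2.

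- n = 30: 4 / 1.291 = 3.098, df 58.
- n = 27: 4 / 1.361 = 2.939, df 52.

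| Level | n = 30 | n = 27 |
|---|---|---|
| One-sided 0.025 | 86.1% | 82.2% |
| Two-sided 0.025 | 78.5% | 73.5% |
| Plan states | 86% | 82.2% |

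The plan's figures reproduce at one-sided 0.025 and not at two-sided 0.025.

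**Step 2: is Holm's second step reached?** Exercise alone versus combined differs by 14.9 − 7.6 = 7.3. With SD 5 and n = 27, noncentrality is 7.3 / 1.361 = 5.364, and power at one-sided 0.025 is 99.95% (99.86% at two-sided 0.025). The second step is nearly always reached.

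**Step 3: weight loss alone versus combined under Holm.** Rule: smaller p-value at 0.025; if rejected, the other at 0.05. A 200,000-run simulation with the shared combined arm agrees with the noncentral-t values.

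| Basis | n = 30 | n = 27 |
|---|---|---|
| One-sided | 86.1% → 92.2% (+6.0) | 82.2% → 89.5% (+7.3) |
| Two-sided | 78.5% → 86.1% (+7.6) | 73.5% → 82.2% (+8.8) |

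**Step 4: error check.** With one true null (combined equal to weight loss alone) and one large effect, n = 27, one-sided, Holm rejected the true null in 4.96% of runs, within 5%.

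**Step 5: sensitivity to the SD of exercise alone.** Setting that arm to 12.5 and the others to 5 (one-sided) makes the first rejection less certain.

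- Weight loss alone versus combined: about 86.2% to 90.7% (n = 30, +4.5) and 82.2% to 87.4% (n = 27, +5.2).
- Exercise alone versus combined, n = 27: 78.9% to about 85.1%.
- Both comparisons significant, n = 27: about 67% to 78%.

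**Step 6: Secondary Hypothesis 2, exercise alone.** One-sided paired t, noncentrality = 7.6 / (12.5/√n): 3.330 at n = 30 and 3.159 at n = 27. At 0.017 this gives 86.0% and 81.6%, which reproduces the stated 86.0% and 82%. At exactly 0.05/3 it gives 85.8% and 81.4%. Under Holm (0.0167, 0.025, 0.05) the simulated power is 94.5% and about 92.4%, gains of about 9 and 11 points. The other two arms have at least 98.6% power at 0.0167 even with SD 12.5, so exercise alone is nearly always tested at 0.05.

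**The case against.** **Bonferroni is not an error.** This stands. It is valid and conservative, and the stated primary power exceeds 80% after attrition. No error rate or conclusion is compromised; the point is one of efficiency.

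**A reader might infer a primary gain of 8 to 11 points.** The documents do not support that. The range fits Secondary Hypothesis 2. For the primary comparison, only the two-sided, n = 27 case (8.8) reaches it. Section 5.9 does not state a two-sided test, and its power figures do not reproduce under one.

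**A reader might infer that the plan's 86% and 82.2% are already Holm powers**, since two-sided Holm gives the same numbers. That is a coincidence of levels: one-sided 0.025 and two-sided 0.05 share a critical value. Section 5.9 describes a fixed 0.025.

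**A reader might infer that the non-independent condition in 5.10 should be deleted so that every family is corrected.** That would bring in Secondary Hypothesis 3, which section 5.9 deliberately tests at 0.05 each. Taking its family as six tests (three outcomes by two contrasts, an assumption), Holm's first step would be 0.05/6 = 0.0083, where PSQI power falls from 78.8% to 50.8% (one-sided, n = 30). Nor do the documents show that Secondary Hypothesis 2 is left uncorrected. Section 5.9 assigns it 0.05/3, and section 5.10 tests it within one repeated-measures ANCOVA, where the three tests would ordinarily share an error estimate. The wording needs clarifying and no more.

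**If success requires beating both single treatments, no adjustment is needed.** This is true: each comparison could then be tested at 0.05. The plan does not state that rule, and it has chosen to adjust. It also leaves unstated how its order-restricted tests relate to the 0.025 comparisons. Neither point removes Holm's advantage over the Bonferroni rule the plan specifies.

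**Conclusion.** The point holds as an efficiency improvement. For the primary and Secondary Hypothesis 2 families, Holm gives the same 0.05 family-wise control under any dependence, rejects everything Bonferroni rejects, and needs no more participants.

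The primary gain is 6.0 points (n = 30) or 7.3 points (n = 27), given one-sided tests, SD 5 in every arm and the assumed reductions. It falls to about 4.5 to 5 points if exercise alone has SD 12.5. If the primary tests turn out to be two-sided, the fixed rule gives 73.5% after attrition and Holm restores 82.2%. For Secondary Hypothesis 2 the gain for exercise alone is about 9 to 11 points, computed with separate paired t-tests as in section 5.9 and not with the ANCOVA of 5.10.

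Holm does not rescue an optimistic SD. With 12.5 in all three arms (n = 27, one-sided), power for weight loss alone versus combined moves only from 21.0% to 28.5%.

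**What to change.** - In 5.9 and 5.10, replace Bonferroni with Holm for the Primary Hypothesis and for Secondary Hypothesis 1: smaller p-value at 0.025 and, if rejected, the other at 0.05.
- Do the same for Secondary Hypothesis 2: ordered p-values at 0.0167, 0.025 and 0.05, stopping at the first non-rejection.
- In 5.10, name these families explicitly, so that the non-independent wording cannot be read against 5.9. Leave Secondary Hypothesis 3 at 0.05 per test.
- State whether the primary tests are one- or two-sided, and restate their power under Holm on that basis.

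**Cost:** text only. No participants, data or type I error control are given up. The one small downside is that simultaneous confidence intervals matching Holm are less simple than Bonferroni intervals, so the plan should say which intervals it will report.
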